16 APPENDIX 3 SUMMARY OF CHANGES

16.1 Version 2.0, 21 Aug 2018

Global changes:

- Neurotrope change of address and logo have been updated.
- Spelling correction: ADCS-ADL-Sev replaces ADCS-ADL-Siv in the list of abbreviations and wherever it occurs in the document
- IRT (Interactive Response Technology) replaces IwRS (Interactive Web Response System) in the list of abbreviations and wherever it occurs in the document.

Inclusion criterion #4 clarification: MMSE-2 inclusion range of 4-15 applies to screening criterion only and may deviate from this range during study participation.

Inclusion criterion #5: The upper limit SIB score for inclusion has been changed from 97 to 93 to optimize measurement of improvement.

Exclusion Criterion #4: Text has been added to describe parameters for eligibility with medical history of cancer: If there is a history of cancer the subject should be clear of cancer for at least 2 years prior to screening. More recent history of basal cell or squamous cell carcinoma and melanoma in situ (Stage 0) may be acceptable after review by the Medical Monitor.

Section 5.3: Since all site personnel are blinded, there is no need to exclude individuals preparing study drug from participation in safety or efficacy assessments. The sentence "The individual designated to prepare the study drug may not participate in any study subject safety or efficacy evaluations." has been removed.

Section 5.5: Text has been added to describe randomization procedure details. The text now reads: "Once all eligibility criteria for the study have been met, and the site has received approval by the Medical Monitor (MM) and Clinical Assessment Technologies (CAT) group, via

the EDC system, the subject can be randomized via Interactive Response Technology (IRT) system.”

Section 6.0, Table 1 Schedule of Activities: A footnote has been added to clarify time window for the screening window. The visit window of ± 2 Days for scheduled study visits does not apply to the screening and randomization period which is a maximum of 28 days.

Section 6.1.2: Text has been clarified to be consistent with Section 6.2.1. The MMSE-2 should be administered and assessed before administering the SIB at screening. For all study visits after randomization, the SIB should be administered first.

Section 6.2.1 Text has been added to describe subject re-screening: Subjects who are screen-failed (e.g. due to clinically significant laboratory abnormality or an active medical condition) may be re-screened if their medical condition stabilizes or improves as assessed by the PI. Subjects who are screen-failed due to MMSE score may be rescreened in 3 months. The Medical Monitor should be consulted prior to re-screening. Subjects who are Screen Failures may be rescreened only once.

Section 14, Appendix 1 Restricted Concomitant Medications: Memantine has been removed from the list of allowed AD medications.

16.2 Version 3.0, 18 April 2019

No changes have been made to study procedures.

The primary efficacy endpoint was described in previous versions as the change in the Severe Impairment Battery (SIB) scale score after 12 weeks of treatment from baseline (taking the change in the average of SIB measures observed during the Week 13 to Week 15 time window from SIB at baseline).

The revised text is: The primary efficacy endpoint is defined as the change from baseline to Week 13 in the SIB total score. This change was made to assure consistency with the primary analysis endpoint as analyzed in study NTRP101-202, for which NTRP101-203 is considered a confirmatory study.

Secondary endpoints were added to analyze the changes from baseline at Weeks 5, 9, 13 and 15 in the SIB total score for subjects enrolled in the MMSE-2 4-9 stratification group and the MMSE-2 10-15 stratification group. Similar analysis methods as the primary endpoint will be used for analysis of these endpoints.

1. INTRODUCTION

This Statistical Analysis Plan describes the planned analyses and reporting for the clinical trial protocol NTRP-101-203, sponsored by Neurotrope, Inc. The reader of this Statistical Analysis Plan (SAP) is encouraged to review the complete protocol as this plan contains only a limited overview of protocol information. The main objective of this plan is to provide details pertaining to statistical methodology, data conventions, and processes used for the analysis of data from this trial.

The format and content of this SAP are structured to provide sufficient detail to meet the requirements specified by the International Conference on Harmonization (ICH) E9: Guidance on Statistical Principles in Clinical Trials. All work planned and presented in this Statistical Analysis Plan will follow the ethical guidelines published by the American Statistical Association (ASA).

The following documents were reviewed in preparation of this Statistical Analysis Plan:

- Version 3.0, protocol 18 April 2019
- ASA Ethical Guidelines for Statistical Practice (2016)
- The Royal Statistical Society: Code of Conduct (2014)
- ICH Guidance on the Structure and Content of Clinical Study Reports (ICH E3, 1996)
- ICH Guidance on the Structure and Content of Clinical Study Reports (ICH E3(R1), 2013)
- ICH Guideline on General Considerations for Clinical Trials (ICH E8, 1997)
- ICH Guidance on the Statistical Principles for Clinical Trials (ICH E9, 1998)
- ICH Guidance on the Statistical Principles for Clinical Trials (ICH E9(R1), 2017)

2. PROTOCOL DESIGN AND OBJECTIVE

2.1 Design Overview

This is a randomized double-blind Placebo-controlled, Phase 2 study comparing bryostatin to placebo for the treatment of moderately severe to severe Alzheimer's disease in subjects not receiving memantine treatment. The study is 15 weeks in duration, including safety and efficacy evaluation 30 days after the last treatment. Eligible subjects will be stratified based on MMSE-2

scores 4-9 vs. 10-15 and will be randomized 1:1 to treatment with 20µg bryostatin or placebo for 12 weeks of treatment. Study drug is administered IV by continuous infusion. The first two doses of study drug will be a loading dose 20% higher (i.e., 24µg) than the assigned dose and will be administered one week apart. Thereafter, the assigned dose of 20µg will commence with the third dose and be administered every other week. Subjects are scheduled to receive seven doses over 12 weeks.

2.2 Treatment Groups

There are two treatment groups in this trial. The two treatment groups to be evaluated in this trial are described below

Table 2-2-1: Treatment Groups

Group	Description
Active Treatment	20 µg bryostatin
Control Treatment	placebo

2.3 Randomization

Once all eligibility criteria for the study have been met, and the site has received approval by the Medical Monitor (MM) and Clinical Assessment Technologies (CAT) group, via the EDC system, the subject can be randomized via Interactive Response Technology (IRT) system. A randomization number will be assigned, and drug for that randomization number will be shipped to the site for twelve weeks of treatment. Randomization and scheduling of the first study drug infusion should be timed to allow for receipt of study drug prior to the scheduled study treatment. The drug kits will be shipped to the individual who will be responsible for kit storage and drug preparation.

2.4 Blinding

All subjects, PIs, and investigational clinical site personnel will be blinded to dose assignment.

Since there is no known antidote to bryostatin, the blind should only be broken in exceptional circumstances and is at the discretion of the PI. The Medical Monitor should be contacted as soon as possible to discuss the situation, but this should not delay any treatment.

In a non-emergency situation, when unblinding is requested, the site should discuss the clinical

circumstances with the Medical Monitor to determine if breaking the blind will alter the subject's treatment. The decision to break the blind is ultimately the decision of the PI. If the blind is broken for a subject, the PI will record the date and reason for breaking the blind in the electronic case report form (eCRF) and study drug treatment will be discontinued. However, the subject will continue to be monitored per protocol for safety and efficacy.

2.5 Study Objective

The primary objective of this study is to evaluate the safety, tolerability and efficacy of bryostatin for the treatment of moderately severe to severe Alzheimer's disease in subjects not receiving concurrent memantine treatment.

2.6 Efficacy Assessments

2.6.1 Primary Efficacy Endpoint

The primary efficacy endpoint is defined as the change from baseline to Week 13 in the SIB total score.

2.6.2 Secondary Efficacy Endpoints

The secondary efficacy endpoints are:

- The changes from baseline at Weeks 5, 9 and 15 in the SIB total score
- The changes from baseline at Weeks 5, 9, 13 and 15 in the SIB total score for subjects in the MMSE-2 4-9 stratification group
- The changes from baseline at Weeks 5, 9, 13 and 15 in the SIB total score for subjects in the MMSE-2 10-15 stratification group
- Individual patient's slope over time in SIB total score evaluated via Weeks 0, 5, 9 and 13.

2.6.3 Exploratory Endpoints:

The exploratory endpoints for this study are:

- Change from baseline in Alzheimer's Disease Cooperative Study - Activities of Daily Living – Severe Impairment Version (ADCS-ADL-Sev) total score
- Change from baseline in Mini Mental State Examination, 2nd edition (MMSE-2) total score

- Change from baseline in 10-point Neuropsychiatric Inventory (NPI) total score
- Clinical Global Impression of Improvement Scale (CGI-I) score

2.7 Safety Assessments

- Treatment emergent AEs and SAEs
- Vital signs, hematology, blood chemistry, and physical examination including body weight
- ECG parameters
- C-SSRS

3. SAMPLE SIZE DETERMINATION AND RATIONALE, STATISTICAL POWER, AND SIGNIFICANCE LEVEL

Based on post hoc analyses of the NTRP 101-202 study for patients not treated with memantine, the SIB for the 20ug bryostatin group demonstrated a mean (SD) increase of 4.5 (6.8) points from baseline by Week 13. In contrast, patients not treated with memantine in the placebo arm showed a decrease in SIB scores at the 13-week time-point from baseline, giving a mean (SD) SIB change of -0.9 (6.7) points. This resulted in group difference in means of the 13-week SIB measure from baseline SIB changes of 5.4 points.

Guided by these post hoc results, power analyses were performed based on 50 patients per treatment arm, and assuming differences of between 4.0 to 5.5 points in the treatment arm-specific means of the primary outcome (e.g. the treatment effect). Table 3-1 below gives the estimated power to detect various treatment effects, assuming a two-sided alpha of 0.05. Based on these analyses, 50 patients per group will give an approximate 83% power to detect a treatment effect of 4.0 points, and an estimated power of 98% to see a treatment effect of 5.5 points. Power calculation was based the two-sample t-test of the group difference in the mean 13-week SIB changes from baseline SIB.

Table 3-1: Power to detect treatment effect sizes of between 4.0 to 5.5 points; 50 patients per group with an available primary efficacy endpoint.

Diff. in Deltas	Power	N1	N2	Two-sided Alpha
4	83%	50	50	0.05
4.5	91%	50	50	0.05

5	95%	50	50	0.05
5.5	98%	50	50	0.05

Power analyses were also performed to determine detectable effect sizes that assume an estimated dropout rate of 25% (e.g. 50 patients per group at a baseline, dropping to 37 patients per group by Week 13). Table 3-2 gives the estimated powers for treatment effects of between 4.5 and 5.5 points, assuming a 25% dropout rate. Note that a minimum treatment effect of 4.5 points can be statistically detected with at least 80% power, given 37 patients per group with a primary efficacy endpoint.

Table 3-2: Power to detect treatment effect sizes of between 4.5 to 5.5 points; 37 patients per group with an available primary efficacy endpoint.

Diff. in Deltas	Power	N1	N2	Two-sided Alpha
4.5	80%	37	37	0.05
5	88%	37	37	0.05
5.5	93%	37	37	0.05

4. INTERIM ANALYSIS

No interim analyses are planned.

5. PRIMARY HYPOTHESIS TO BE TESTED

The primary hypothesis to be tested for this study is below:

H_0 : $\mu_{Active} = \mu_{Control}$ (i.e. mean change from baseline in SIB total score between the two groups is the same)

H_1 : $\mu_{Active} \neq \mu_{Control}$ (i.e. mean change from baseline in SIB total score between the two groups is different)

6. ANALYSIS POPULATIONS

6.1 Full Analysis Set

The Full Analysis Set (FAS) used for efficacy analyses is defined as all randomized subjects who received at least one dose of study medication and who have at least one post-baseline efficacy assessment.

6.2 Safety Analysis Set

The Safety Analysis Set (SAS) is defined as all randomized subjects who received any study medication (either partial or completed infusions of bryostatin or placebo).

6.3 Completer Analysis Set

The Completer Analysis Set (CAS) is defined as all randomized subjects who completed 12 weeks of treatment, and who have a week 13 SIB assessment.

7. DATA CONVENTION AND RELATED DEFINITIONS

7.1 Baseline Definition

For all parameters, baseline will be defined as the last available value before the randomized treatment.

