Confidentiality of all information received or developed in connection with this protocol will be maintained by me, as well as all other personnel involved in the study who are employed by me. By signing this protocol, I confirm that I have read and agree to conduct the study as outlined in the protocol and in compliance with Good Clinical Practice, the Declaration of Helsinki as amended and all other applicable regulatory requirements.

Printed name of PI: _____

Signature

Date

STUDY CONTACT INFORMATION

Sponsor : Neurotrope, Inc.
[name].
[name]
[name]
[contact]
[contact]

[name] Acting Chief Medical Officer
Neurotrope, Inc.
[contact]
Email [contact]

[name] Executive Director, Clinical Operations
Neurotrope, Inc.
[contact]
Email: [contact]

Study Administrative Structure

Clinical Research Organization

Worldwide Clinical Trials

Operational Headquarters
[name]
[name]
[name]
[contact]
Corporate Headquarters
[name]
[name]
[contact]

Study Medical Monitor/Emergency Contact Information

[name]
Worldwide Clinical Trials
[contact]:
Email: [contact]

Central Laboratory

Eurofins Lancaster Laboratories
[name]
[name]
[contact]

Central ECG

eResearch Technology, Inc. (ERT)
[name]
[name]
[contact]

PROTOCOL SYNOPSIS

Name of Company: Neurotrope, Inc.	Name of Study Medication: Bryostatin 1	Name of Active Ingredient: Bryostatin 1
Title of Study: A Randomized, Double-Blind, Placebo-Controlled, Confirmatory Phase 2 Study Assessing the Safety, Tolerability and Efficacy of Bryostatin in the Treatment of Moderately Severe to Severe Alzheimer’s Disease Subjects Not Receiving Memantine Treatment		
Study center(s): Approximately 30 sites in United States (US)		
Protocol Number: NTRP-101-203		
Study Duration: Approximately 12 months	Study Phase: 2	
Objective: Primary objective: To evaluate the safety, tolerability, and efficacy of bryostatin 1 (hereafter referred to as bryostatin) for the treatment of moderately severe to severe Alzheimer’s disease (AD).		
Study Drug: Bryostatin 1 or matching Placebo		
Route of Administration: Intravenous by continuous infusion over 45±5 minutes		
Number of Subjects: 100 randomized subjects (approximately 145 subjects screened)		

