2 CLINICAL TRIAL DATA

2.0 Oncology Data

Safety data are available from published clinical studies of bryostatin for the treatment of cancer. Altogether, over 1400 oncology subjects received bryostatin, mainly under NCI's IND # 42,780, with exposures to bryostatin in both single and combination agent studies. About 584 subjects received bryostatin as monotherapy, with dose levels ranging from 5µg/m² to >180µg/m². Most subjects in both the monotherapy and combination therapy studies received bryostatin at doses >25µg/m², most often as 1-hour infusions administered at various time intervals from weekly infusion to continuous infusions for 72 hours. Most studies were repeated dose studies where subjects received treatment for several weeks (See Investigators Brochure).

Adverse events occurring in the single agent studies that resulted in discontinuation from the studies were myalgia (28 subjects), acute transient reaction (dyspnea, flushing, hypotension, and bradycardia; 4 subjects each), phlebitis (attributed to ethanol in the formulations, 6 subjects), fatigue (3 subjects), and 1 subject each with bacteremia, chest pain, dehydration, dysphagia, hematuria, nausea, skin rash, subclavian vein thrombosis, thrombocytopenia, and vomiting. The following AEs were associated with death in the single agent trials: cardiac arrest (2), hypotensive with evidence of renal and hepatic failure (1), perforated gastric ulcer (1), renal function decline with cardiac arrest and perforated gastric ulcer (1; PIs considered not related to bryostatin), and sudden death (1; PIs considered likely to be cardiovascular event). Relatedness to bryostatin treatment was not assessed except where noted.

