6.0 Table 1 - Schedule of Activities

		NTRP101-203										
Week	Screening	0	1	2	3	5	7	9	11	13	15/ET	
Day (±2 days)	(Days -28 to -2) ^d	0	7	14	21	35	49	63	77	91	105	
Dose	Rand	1	2		3	4	5	6	7			
Informed Consent	X											
Medical history	X											
Demographics	X											
Rosen-modified Hachinski Scale	X											
SIB	X ^a					X*		X*		X	X	
MMSE-2	X					X*		X*		X	X	
ADCS-ADL-Sev ^b	X					X*		X*		X	X	
NPI ^b	X					X*		X*		X		
CGI-I						X*		X*		X		
CSSRS	X			X			X*			X		
Labs ^{^^}	X			X			X*			X		
ECG	X (x3)			X			X			X		
PE	X						X* ⁺			X		
Vitals	X	X ^c	X ^c	X	X ^c	X ^c	X ^c	X ^c	X ^c	X ^c	X	X
Randomization		X ^a										
Confirm Eligibility	X [◊]	X										
Study Drug Dosing		X	X		X	X	X	X	X			
Adverse Events	X	X	X	X	X	X	X	X	X	X	X	
Con meds	X	X	X	X	X	X	X	X	X	X	X	

^aBaseline SIB administered during screening must be done within 3 weeks of the first dose of study drug. If the screening period exceeds 3 weeks, the SIB should be repeated on the day of first dose, prior to dosing; * before dose; ^^Labs: CBC including differential, coagulation, clinical chemistry, TSH at screening (B12, T-3 and T-4 if TSH abnormal), CPK at screening and event of myalgia, βhCG if indicated, HbA1C if clinically indicated; [◊] CT scan if necessary per inclusion criterion #6; ⁺ abbreviated physical examination; ^a Randomization after initial screening procedures indicate eligibility; ^b The ADCS-ADL-Sev and NPI may be administered via telephone at the discretion of the investigator, within the allowed time window for the scheduled visit; ^c Vital signs prior to infusion, then at 30, 60 and 90 minutes from start of the infusion (+/- 5min). ^dThe visit window of ±2 Days does not apply to the Screening and Randomization period which is a maximum of 28 days.

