8. STATISTICAL METHODS

All data collected during this study will be presented in subject data listings.

All statistical analyses will be performed using SAS[®] for Windows, version 9.4 or later. For continuous variables, descriptive statistics (n, mean, standard deviation, median, minimum and maximum) will be presented by treatment group. For categorical variables both frequencies and percentages will be presented by treatment group.

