8.3.1 Adverse Events

Adverse events will be coded using the most recent version of Medical Dictionary for Regulatory Activities (MedDRA). Treatment Emergent AE's (TEAE) are defined as events with an onset on or after the first randomized treatment. TEAEs will be summarized by treatment group, System Organ Class, and preferred term. The following TEAE summaries will be provided:

- Overall (*i.e.*, regardless of severity or relationship to treatment)
- By severity grade (mild, moderate, severe, life threatening or death for SAEs)
 - By relationship to clinical trial treatment (definitely related, probably related, possibly related, unlikely related, unrelated)

Unless otherwise specified, at each level of subject summarization, a subject will be counted only once. If there is more than one occurrence of an event, the event of the worst severity or the worst-case relationship category will be summarized.

In addition, separate summaries of serious adverse events, and adverse events resulting in discontinuation of study treatment will be presented.

AEs leading to premature discontinuation of clinical trial treatment, AEs that lead to study discontinuation, AEs that lead to death and Serious Adverse Events (SAEs) will also be summarized by treatment group and relationship.

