8.3.4 Vital Signs

Tabulations of raw data and change from baseline values will be presented by time point for each vital sign parameter.

Tabulations will include the number of observations, mean, standard deviation, median, and minimum and maximum values. For change from baseline summaries, subjects with an undefined change from baseline, because of missing data, will be excluded.

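### At doses 2 to 7 the post-start vital signs are compared with a pre-first-dose baseline 1 to 11 weeks old, so no planned summary by arm shows the spread or extremes of the within-visit change

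*SAP*

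**What the plan says.** SAP 7.1 gives a single rule: "For all parameters, baseline will be defined as the last available value before the randomized treatment". SAP 8.3.4, like Protocol 9.8.4, then states: "Tabulations of raw data and change from baseline values will be presented by time point for each vital sign parameter". The summary statistics are n, mean, SD, median, minimum and maximum, and SAP 8.3 has safety data summarized by treatment.

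On dosing days the schedule (Protocol 6.0, repeated in SAP Appendix 1) asks for "Vital signs prior to infusion, then at 30, 60 and 90 minutes from start of the infusion (+/- 5min"). SAP 2.1 sets the number of infusions: "Subjects are scheduled to receive seven doses over 12 weeks". The Protocol synopsis gives the route and length: "Intravenous by continuous infusion over 45±5 minutes".

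Neither document defines a change from the same visit's pre-infusion reading. Laboratory values, physical examination and ECG each have shift tables (SAP 8.3.2.2, 8.3.3 and 8.3.5). Vital signs have none.

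**The concern.** The three post-start readings are timed around peak exposure. Protocol 2.1.6 reports that the median time of maximum concentration in the previous Alzheimer's study was the end of the 45-minute infusion. The other physiological measures scheduled on a dosing day (Week 7 laboratory samples, ECG and abbreviated examination, Protocol 6.2.7) are taken before dosing. The vital signs are therefore the only scheduled physiological readings after an infusion has started.

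The background gives a reason to look at them. Among adverse events leading to discontinuation in the oncology single-agent studies, Protocol 2.0 lists "acute transient reaction (dyspnea, flushing, hypotension, and bradycardia; 4 subjects each"). An event of that kind is a short-lived change within one visit, in a few subjects. It would show in the spread and extremes of the within-visit change more than in its mean.

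A change score that refers back to the first dose adds the subject's variation between visits to the acute change. What is at stake is how clearly a safety table shows infusion-related changes in blood pressure and pulse. No efficacy conclusion is involved.

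**Working it through.** The plan states no vital-sign SD, correlation or detectable change, so there is no figure of its own to reproduce. The check has three steps.

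**1. Which readings are affected.** Doses fall on Days 0, 7, 21, 35, 49, 63 and 77.
- Post-start readings per subject: 7 infusions × 3 = 21.
- At dose 1 the last value before treatment is the same-day pre-infusion reading, if taken, so those 3 readings already have a same-visit reference.
- Doses 2 to 7: 6 × 3 = 18 readings, with a reference nominally 7 to 77 days old (1 to 11 weeks, visit window ±2 days).
- Timing is from the start of a 45 ± 5 minute infusion. The 30-minute reading falls during it and the 60- and 90-minute readings after it, so 6 of the 18 are taken while drug is running.

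**2. What the planned tables can and cannot give.** Let B be the study baseline, P the pre-infusion value at a later visit, and T a post-start value at that visit. If the same subjects have both P and T,

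mean(T − B) − mean(P − B) = mean(T − P).

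The mean acute shift is therefore recoverable by subtraction, from either the change means or the raw means. In a simulated data set of 50 subjects both routes gave −10.68. The SD is not recoverable this way: in the same data it was 10.7 for T − B and 6.6 for T − P. The minimum, maximum and individual values of T − P also do not follow from the separate summaries of T and P.

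**3. How much noisier the planned change is.** With a common SD σ per reading and correlation r between two readings, SD of change = σ√(2(1 − r)). The ratio of the planned change to a same-visit change is then √((1 − r_between)/(1 − r_within)), which does not depend on σ. All inputs here are assumptions.

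| r within visit | r between visits | Ratio of SDs |
|---|---|---|
| 0.7 | 0.6 | 1.15 |
| 0.8 | 0.7 | 1.22 |
| 0.8 | 0.6 | 1.41 |
| 0.8 | 0.5 | 1.58 |
| 0.9 | 0.6 | 2.00 |
| 0.9 | 0.5 | 2.24 |

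If the two correlations were equal (both 0.7, say), the ratio would be √(0.3/0.3) = 1.00 and nothing would be lost in precision. The range 1.15 to 2.24 thus assumes that readings an hour or so apart correlate more closely than readings weeks apart, by at least 0.1.

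In mmHg, assuming σ = 15 and r within = 0.8:
- Same-visit reference: 15 × √0.4 = 9.5.
- First-dose baseline: 15 × √0.6 = 11.6, 15 × √0.8 = 13.4 and 15 × √1.0 = 15.0, for r between of 0.7, 0.6 and 0.5.
- The 95% half-width for the difference between arms, 1.96 × SD × √(2/n), is 3.7 versus 4.6, 5.3 and 5.9 mmHg with 50 per arm.
- With 37 per arm (the plan's 25% dropout case) it is 4.3 versus 5.3, 6.1 and 6.8 mmHg.

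**The case against.** A reader might infer that acute infusion effects will be hidden from view. The documents do not support that, for four reasons.

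- Raw values are tabulated by time point, so the mean acute shift in each arm can be read off by subtraction, and the raw minimum shows the lowest pressure or pulse at each reading.
- Drift common to both arms cancels in the comparison with placebo.
- SAP 8 states: "All data collected during this study will be presented in subject data listings". Every pre-infusion and post-start value will be available, and individual falls can be counted by hand.
- Clinical reactions have their own route through adverse-event recording at every visit, and systemic hypersensitivity reactions go to the Medical Monitor at once (Protocol 7.6.1).

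The background is also less alarming than one line suggests. Most oncology subjects received more than 25 µg/m², and the previous Alzheimer's study saw no apparent group differences in most vital signs (Protocol 2.1.4). The documents report no blood-pressure drift. The SAP plans no count of falls beyond a fixed size, so a false-alarm rate for such a count would describe an analysis nobody has proposed. Finally, SAP 10.2 names the vital-sign tables only in outline, so a within-visit table could be added without contradicting the SAP.

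All of this limits the point but does not remove it. Subtraction gives only the mean, and only when the same subjects have both readings. The placebo comparison removes common mean drift but not the added variance. Listings are not a summary by arm. Adverse-event reports do not describe the size of measured changes.

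One could also read 7.1 as allowing a fresh baseline at each dose, since it does not say first. The SAP's definition of treatment-emergent events does say it: "events with an onset on or after the first randomized treatment". A single pre-first-dose baseline is the natural reading of 7.1, and the missing word is worth adding.

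**Conclusion.** The point holds as a modest gap in safety reporting. The stated rule gives a noisier measure of acute effect at 6 of 7 infusions than data already collected would allow. No planned summary by arm shows the SD, minimum, maximum or individual size of the within-visit change.

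The count of 18 of 21 readings follows from the schedule and from reading 7.1 as the value before the first dose. The SD ratio of 1.15 to 2.24 rests wholly on assumed correlations and would shrink towards 1 if between-visit correlation approached within-visit correlation.

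The point does not extend to the trial's conclusions. Safety data carry no hypothesis tests (Protocol 9.3), and the primary efficacy analysis, sample size and conduct are unaffected.

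**What to change.** - In SAP 7.1, define baseline as the last available value before the first dose of randomized treatment.
- In SAP 8.3.4, add for the 30-, 60- and 90-minute readings the change from the same visit's pre-infusion value, by arm, dose number and time point, with n, mean, SD, median, minimum and maximum.
- Also in 8.3.4, add each subject's largest within-visit fall in systolic pressure and in pulse, summarized by arm.
- Keep the study baseline for the pre-infusion readings, where it shows slow change across visits.

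The cost is a short SAP edit and some extra descriptive output (arm by dose by three times for each parameter, plus the per-subject summary). All the data are already scheduled for collection, and no procedure changes.
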